3. STUDY DESIGN

Activities to meet Aim 1. We will evaluate MMORE in a two-group randomized controlled design comparing treatment as usual (TAU) in partner maternity care practices with TAU + MMORE.

Participants will be 150 English-speaking consenting pregnant women aged 18 years and over who have a confirmed singleton pregnancy and are receiving perinatal services and medication for opioid use disorder at partner maternity care practices. We will aim to recruit women in their 2nd/early 3rd trimester of pregnancy.

After completion of the baseline assessment, consented participants will be randomly assigned to participate in the 8-session virtual yoga-mindfulness group intervention or to receive TAU only.

All intervention participants will be provided with a unique password-protected access link to the digital support materials, as well as detailed instructions for how to access the materials. A unique study code will allow us to monitor individual participant use of the support modules for analytic purposes.

All consented participants will complete assessments at baseline, post-intervention (8 weeks for TAU participants) and 3 months postpartum. Participants will complete assessments via a secured, de-identified and password-protected link accessed either on a study-provided laptop computer at a scheduled practice visit or via a protected email link to the user for completion at home or on another secure device with Internet access. Assessments will take approximately 20 minutes to complete. Based on formative data from phase 1 of this project, and other work the research team has conducted with the target population, we anticipate most women will have some access to the Internet either via a mobile phone, tablet, or home computer. If a participant cannot complete an assessment online, a paper version will be provided. The study staff will track ways that participants complete assessments. Participants will receive local gift cards for completion of each assessment.

Activities to meet Aim 2. All study participants (TAU and TAU+MMORE) will complete brief mobile assessments at the end of each week of their assigned cohort period. Assessments will be completed using either a mobile device or computer. Participants will receive a prompt (near end of the week) to complete the assessment. The encrypted, password-protected weekly brief assessment will include items to assess the following:

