We have developed a safety protocol (overseen by Drs. [name] and [name]) to ensure strict attention to safety for women participating in the yoga intervention. As with other gentle yoga protocols, the safety protocol will include specific directions by the Intervention Instructor that participants do not have to partake in any of the poses or activities that feel uncomfortable, and adjustments will be made as needed to minimize discomfort for those participants that would like such adjustments. Lead Instructor [name] has over six years of experience leading trauma-sensitive yoga protocols with pregnant incarcerated women, a vulnerable population similar to that for the proposed project.

The Lead Instructor will complete the Session Event Checklist after each intervention session to denote any adverse events (non-serious and serious) that take place during the intervention sessions. Participants will complete the Intervention Experience Form at the end of each session to document experience of any adverse events including physical experiences (e.g., shortness of breath, pain, increased or decreased infant movement, or other discomfort experiences during the session) and psychological experiences (e.g., emotional flooding, uncontrollable crying). At the end of each intervention week, all participants will also complete a Weekly Monitoring Form that will include items related to any additional experience of adverse physical or psychological events. The project coordinator will administer the Weekly Monitoring Form by telephone or e-mail.

In the event that a study participant lapses or relapses during the study period, cases will be handled on an individual basis, which may be largely determined by the procedures of the partner maternity care practice in terms of preference for ongoing care. A lapse/relapse will not necessarily lead to participant discontinuation in the study.

Treatment as Usual. Treatment as usual is operationalized as the integrated medication assisted treatment being provided at the partner practice as part of the New Hampshire State Targeted Response 21st Century Cures initiative. Such treatment includes medication for opioid use disorder, individual and/or group counseling, and case management.

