6.2.2 Enrollment, Baseline, and/or Randomization

Enrollment

In this study, the enrollment date will be the date that all of the screening criteria were met, and the individual consents to participate.

Baseline Assessments

Participants will complete the baseline assessment upon consenting to participate in the study. The project coordinators will administer the baseline assessment to the participant through a secure online survey. For participants who do not wish to complete the survey online, the project coordinator will arrange for either a phone interview with the participant to complete the survey or will mail the participant the survey along with a self-addressed and stamped envelope for the participant to return the survey. Both forms of the assessment will be coded with a unique study ID.

Randomization

Following baseline completion, participants will be randomized to condition by the lead project coordinator. The lead project coordinator will meet via phone with participants assigned to the MMORE condition to explain the condition. Participants in the MMORE condition will receive a secure password-protected access to the digital companion features.

Randomization will be conducted via permuted blocks. Once 8-10 participants have enrolled, an intervention will commence for that cohort. The randomization block size would be random, with blocks of size 4, 6, and 8. In thinking about how best to implement our group randomization plan in the context of the reality of recruitment of this high-risk target population, we have developed a plan of ongoing recruitment and starting a new group at least every 8 weeks. With a conservative recruitment

rate of 12 participants per month, we do not anticipate a good deal of differential lag-time between recruitment into the study, completion of baseline, randomization, and start of a new group.

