9.2 Sample Size and Randomization

Sample Size.

Aim 1: For the longitudinal models of binary outcomes (abstinence, retention), assuming a within-person correlation of 0.5, there will be 80% power to detect difference between arms in the proportion retained at the 3 timepoints if the average percentage retained in the TAU arm is 60%, and the average percentage retained in the MMORE arm is 79.2%. Similar power is obtained if the TAU arm has a retention percentage of 70% while the MMORE arm has a percentage of 87% across the three timepoints. In terms of comparing abstinence longitudinally, there will be 80% power to detect a difference between arms in the percentage abstinent at the 3 timepoints if the average percentage abstinent in the TAU arm is 80% while in the MMORE arm is 94%. Power for the comparison of number of weeks abstinent during the 8-week intervention period will be 80% (at the two-sided 0.05 significance level) for differences between arms that are 0.52 times a standard deviation or more. Analyses testing for differences between arms in changes between baseline and 8-weeks, will have 80% power to detect differences that are 0.40, 0.52, and 0.61 times a standard deviation, assuming within-person correlations of 0.7, 0.5, and 0.3, respectively. We will aim to recruit 150 participants to allow for attrition (20%).

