9.6 Data Analyses

Aim 1

Primary analysis: The difference between treatment arms with respect to likelihood of opioid abstinence and remaining in treatment will be evaluated by logistic generalized estimating equations (GEE). Since these binary outcomes will be evaluated at the 8-week as well as the 3-month postpartum time points, these GEE models will account for the non-independence of repeated measurements within individual. An indicator of treatment arm, time point, as well as an interaction between treatment and time point will be included as predictors in the model along with baseline covariates. Significant differences between the arms will be tested via contrasts involving the treatment*time point interaction term that compare the outcomes at each time point.

The impact of *MMORE* on treatment retention (number of weeks retained) will be evaluated via two-sample t-test if the distribution appears symmetric, but a non-parametric Wilcoxon rank sum test will be used otherwise.

Aim 2

Primary analysis: Analyses of mechanisms of effect of *MMORE* will be performed via parallel process growth models fit via structural equation models, and mediated effects between treatment assignment and outcome will be examined for the following mediator-outcome pairs: craving-abstinence, mindfulness-craving, mindfulness-treatment retention, depression-treatment retention, anxiety-treatment retention, stress-treatment retention, and mindfulness-pain. Since each mediator and outcome variable will be collected at multiple time points, latent intercept and slope effects can be estimated (as in latent growth curves). The parallel process growth models then examine mediation of the effect of an individual-level variable (treatment assignment) on the latent slope of the outcome variable by the latent slope of the mediator variable. For each mediator-outcome pair, a parallel process growth curve model will be fit including both the direct effect of treatment assignment to *MMORE* on the latent slope of the outcome, as well as the indirect effect of *MMORE* on slope of the outcome through the slope of the mediator. Estimates of path coefficients for each individual path as well as of the indirect effect along with a 95% bootstrap confidence interval will be obtained.

To examine these associations we will implement a newly developed modeling strategy called dynamic structural equation models (DSEM). DSEM like non-dynamic SEM are a modeling

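### MMORE is delivered in session groups, but the Aim 1 tests and the power calculation assume no correlation between women in the same group; if there is any, intervals are too narrow and power is below 80%

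*Combined protocol and SAP*

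**What the plan says.** Section 3 describes MMORE as an "8-session virtual yoga-mindfulness group intervention". Sections 6.2.2 and 9.2 describe how groups form: "Once 8-10 participants have enrolled, an intervention will commence for that cohort". Women are randomised individually in permuted blocks. The comparator has no study group: "Treatment as usual is operationalized as the integrated medication assisted treatment being provided at the partner practice" (section 5.1). That care can include group counselling, which is open to both arms.

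For Aim 1, section 9.6 plans logistic GEE models for abstinence and retention that "account for the non-independence of repeated measurements within individual". The predictors are arm, time point, their interaction and unlisted baseline covariates. Weeks retained is compared by a two-sample t-test or a Wilcoxon rank sum test.

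The power statement for the binary outcomes in section 9.2 is made "assuming a within-person correlation of 0.5". For retention it claims 80% power when the rates, averaged over three time points, are 60% under TAU and 79.2% under MMORE. It names no other correlation. The increase to 150 women is explained by 20% attrition alone.

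Nowhere do the documents give a session-group ICC, a design effect, a group random effect or a variance clustered on group. The dynamic SEM for Aim 2 has within-individual, between-individual and between-time levels, but no session-group level.

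**The concern.** Women who attend the same eight sessions share group dynamics, timing and possibly an instructor. Their outcomes may therefore be more alike than those of women in different groups. This can arise in the MMORE arm and has no counterpart study group in the TAU arm.

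A GEE clustered on the woman has a sandwich variance that is robust to correlation among her own repeated measurements. It gives no protection against correlation between women. The t-test and Wilcoxon test have the same gap. With positive group correlation, the variance of the MMORE mean is understated. The co-primary outcomes would then be reported with intervals that are too narrow, and the sample size would not support the stated power.

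**Working it through.** **Inputs from the documents.** 150 recruited with 20% attrition gives 150 × 0.8 = 120 evaluable, or 60 per arm at equal allocation. There are 3 time points and a within-person correlation of 0.5. The test level is stated "at the two-sided 0.05 significance level" for the weeks-abstinent comparison and is assumed to be the same for the binary outcomes.

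**Assumed inputs.** ICC 0.01 to 0.10, with the group effect constant over time. MMORE group size m is 5 if the 8-10 women per cohort count both arms, and 10 if they count MMORE women only; the text does not say which.

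**Reproducing the stated power.** Averaging 3 correlated measurements multiplies the variance by v = (1 + 2 × 0.5)/3 = 0.667, so effective n = 60/0.667 = 90 per arm. For 60% against 79.2% (mean 69.6%):
- SE under the null = √(0.696 × 0.304 × 2 × 0.667/60) = 0.0686
- SE under the alternative = √((0.24 + 0.1647) × 0.667/60) = 0.0671
- power = Φ((0.192 − 1.96 × 0.0686)/0.0671) = 80.5%

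The same method gives 79.8% for 70% against 87%, and 80.3% for 80% against 94%. All three match the stated 80% with zero group correlation, and 120/0.8 = 150 leaves no allowance for groups.

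**Adding group correlation in the MMORE arm only.** The MMORE factor becomes v + (m − 1) × ICC. Averaging over time reduces within-person noise but not a persistent group effect. For m = 5 and ICC 0.05 the added term is 4 × 0.05 = 0.20:
- SE under the null = √(0.2116 × (1.333 + 0.20)/60) = 0.0735
- SE under the alternative = √((0.24 × 0.667 + 0.1647 × 0.867)/60) = 0.0710
- power = Φ((0.192 − 1.96 × 0.0735)/0.0710) = 75.0%

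Power of a test that holds its 5% level, for 60% against 79.2%:

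| ICC (assumed) | 5 per group | 10 per group |
|---|---|---|
| 0 | 80.5% | 80.5% |
| 0.01 | 79.4% | 78.0% |
| 0.05 | 75.0% | 68.5% |
| 0.10 | 69.8% | 58.6% |

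At ICC 0.05 the other two binary scenarios give 74.4% and 75.2% (5 per group), or 68.0% and 69.0% (10 per group).

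**Type I error of the planned, unadjusted test.** The ratio of true to assumed variance is (1.333 + (m − 1) × ICC)/1.333. At ICC 0.05 it is 1.15 for m = 5 and 1.3375 for m = 10, so the true SE is 1.07 or 1.16 times the model SE. Then 2 × (1 − Φ(1.96/√1.15)) = 6.8%, and 2 × (1 − Φ(1.96/√1.3375)) = 9.0%.

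**Sensitivity to attrition.** Losing 20% turns groups of 5 and 10 into 4 and 8 analysed women. At ICC 0.05, power is then 76.3% or 71.1%, and type I error 6.3% or 8.1%.

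**Sensitivity to the variance form.** With the unpooled SE, power is Φ(0.192/SE − 1.96). The starting value is 81.7%, falling to 77.1% (m = 5) or 71.8% (m = 10) at ICC 0.05. The loss is smaller because the MMORE arm has the smaller binomial variance (0.1647 against 0.24).

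**The case against.** The strongest objection is that the harm depends on an ICC that the documents do not supply. The primary outcomes come largely from urine toxicology and counselling attendance at the practice, and nothing in the plan shows that a virtual session group would correlate these strongly. At ICC 0.01 the effect is 1 to 3 points of power. This stands, so the point is conditional. It does not remove the gap, because the plan in effect sets the ICC to zero without saying so.

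Several stronger readings are tempting but unsupported:

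- **That the standard errors are certainly wrong.** They are too small only if group correlation is positive. If MMORE affected no one, individual randomisation would protect the test. Type I inflation needs groups that differ in effect around a zero average.
- **That TAU women are fully independent.** TAU can include group counselling (sections 5.1 and 5.3.1). What can be said is that they share no study group. Because counselling is available in both arms, it is not a source of clustering peculiar to MMORE.
- **That a shared instructor must create clustering.** Section 5.1 has the lead instructor delivering sessions, while section 10.3.1 has two more being trained. If one person taught every group, instructor would not distinguish groups.
- **That clustering is the main threat to the 80%.** Section 9.6 tests each time point separately, whereas section 9.2 powers an average over three. A single-time-point contrast with 60 per arm has about 63% power for 60% against 79.2% before any clustering. That is a separate issue.
- **That practice must be added as a covariate.** This is a different, precision-related choice. Section 9.6 already allows unlisted baseline covariates, and the number of practices is not given. The abstinence scenario implies only about 60 × 0.20 + 60 × 0.06 = 15.6 non-abstinent women.
- **That a logistic mixed model is interchangeable with the GEE.** It estimates an odds ratio conditional on group, whereas the GEE estimates a marginal one.

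**Conclusion.** The concern holds in conditional form. The design is partially nested, and neither the Aim 1 analyses nor the power calculation allows for session groups. If outcomes correlate within groups, the planned intervals are too narrow and the stated power is too high. The effect is negligible at ICC 0.01. At ICC 0.05 it is about 5 to 12 points of power and a type I error of roughly 7% to 9%. At ICC 0.10 the loss is about 11 to 22 points.

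These figures assume 60 evaluable women per arm, 5 or 10 MMORE women per group, a group effect stable over time, clustering in one arm only, and a normal approximation. Applying a full cluster-trial design effect to both arms would overstate the loss. With attrition the analysed groups would be smaller and the loss somewhat less; a t reference based on few groups would lower power further. Confidence is high that the plan omits session groups and moderate about how much this matters.

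**What to change.** - **Data.** Record session group ID and instructor for every MMORE woman. Attendance is already tracked by study ID (section 5.4), so this adds little. State whether the 8-10 women per cohort count both arms or MMORE only.
- **Section 9.6, binary outcomes.** Define the GEE cluster as the session group for MMORE women and the individual for TAU women. Use a small-sample-corrected sandwich variance and a t reference. The correction is needed because 75 MMORE women form only about 15 groups of 5, or 7 to 8 groups of 10.
- **Section 9.6, weeks retained.** Use the same group-level variance in place of a test that assumes independent women.
- **Section 9.2.** Restate power over an assumed ICC range such as 0.01 to 0.10.

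The cost is SAP wording, one or two recorded variables, slightly wider intervals and a less favourable stated power. Some of this is paid even if the ICC is zero. For the 0.52 SD comparison, t-based power goes from 80.6% to 79.2% (5 per group) or 77.0% (10 per group), because the degrees of freedom then depend on the number of groups. Keeping the stated power at ICC 0.05 by recruitment alone would need about 150 × 1.15 = 173 or 150 × 1.3375 = 201 women. The request here is to state the power honestly, not to enlarge the trial.

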Early postpartum period presents increased risk for MOUD discontinuation. Even when treatment is initiated, there is a high rate of discontinuation, particularly during the early postpartum period. In a recent systematic review, prenatal discontinuation rates ranged from 0-33%, and postnatal rates from 26-64%. In a well-established integrated perinatal obstetric-MOUD program in NH, MOUD discontinuation was 40% at 3 months postpartum, with the greatest drop-off evident between 6 weeks and 3 months postpartum. Much of the extant literature focuses on methadone discontinuation and there is a need for research on treatment retention among women receiving buprenorphine, particularly during the early postpartum period. The proposed project aims to address this research gap.

Pain management is complicated for pregnant and parenting women with OUD. Pain management, already a common concern for intrapartum and postpartum care, is complicated in the context of opioid dependence. In addition to natural pregnancy-related pain (e.g., leg and lower back pain, musculoskeletal pain), chronic pain (e.g., endometriosis, traumatic injury) is often part of the clinical portrait of women with substance use disorders. The limited literature regarding perinatal pain management for women with OUD indicates that pregnant women on MOUD can experience cross-tolerance for other pain medications, requiring more medication to manage pain. Increased sensitivity to pain (hyperalgesia) is also a hallmark of long-term opioid use, also necessitating use of more intensive pain management strategies. Mental health conditions can exacerbate patients' experiences of pain, and sleep quality, a critical component of wellbeing, is negatively affected by pregnancy and opioid dependence. Poor sleep quality is associated with increased sensitivity to pain and is a risk factor for relapse. Several studies suggest that pain management for women with OUD deteriorates postpartum, such that women on MOUD experienced increased pain postpartum compared with opioid-naïve women. Under-treatment of pain can significantly increase risk of relapse. Accessible non-pharmacological approaches to pain management may offer an important adjunct to recovery support for pregnant and parenting women with OUD.

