4. SELECTION AND ENROLLMENT OF PARTICIPANTS

4.1 Inclusion Criteria

Eligible participants will be women, 18 years of age or older, English-speaking, carrying a singleton pregnancy, and receiving medication for OUD treatment as part of prenatal care at a partner maternity care practice.

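### Section 9.2 gives 80% power for a time-averaged comparison, but Section 9.6 tests each time point separately, where power is about 58% to 64%, and names no test statistic or sparse-cell fallback

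*Combined protocol and SAP*

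**What the plan says.** Section 9.2 (Sample Size, Aim 1) describes longitudinal models of binary outcomes, "assuming a within-person correlation of 0.5", and says of retention that "there will be 80% power to detect difference between arms in the proportion retained at the 3 timepoints". The rates behind this are averages of 60% under TAU and 79.2% under MMORE. It gives similar power for 70% against 87% retained. For abstinence it gives 80% power "if the average percentage abstinent in the TAU arm is 80% while in the MMORE arm is 94" percent. All three statements concern percentages averaged over three time points. No formula or test is named.

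Section 9.6 (Aim 1, primary analysis) specifies a logistic GEE with arm, time point, their interaction and baseline covariates, evaluated at two time points: 8 weeks and 3 months postpartum. Its testing rule is: "Significant differences between the arms will be tested via contrasts involving the treatment*time point interaction term that compare the outcomes at each time point". It does not say whether the test is Wald or score, whether one or both time points must be significant, or what happens if every woman in an arm is abstinent or retained at a time point.

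**The concern.** The power statement and the test do not describe the same comparison. An average over correlated time points is more precise than a single time point, so power for the average does not carry over to the separate contrasts.

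The interaction model also gives each arm-by-time cell its own logit. At 94% abstinent with 60 women, the MMORE cell is expected to hold 60 × 0.06 = 3.6 non-abstinent women. With so few failures a Wald test on the log-odds scale is conservative. With none, the odds ratio is infinite and the contrast has no finite estimate.

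At stake are the power claimed for both primary endpoints and, for abstinence, an unplanned choice of method after the data are seen.

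**Working it through.** **Inputs.** Section 9.2 gives 150 recruited, 20% attrition, correlation 0.5, three time points and the three rate pairs. Equal allocation (Section 4.3) leaves 150 × 0.8 / 2 = 60 per arm. Alpha is taken as 0.05, "at the two-sided 0.05 significance level"; 9.2 prints this for the weeks-abstinent comparison, and it is assumed here for the binary models. Exchangeable correlation is assumed. Baseline covariates are not modelled.

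**Step 1: reproduce the printed 80%.** The mean of T correlated time points has variance factor (1 + (T − 1)r)/T. With T = 3 and r = 0.5 this is 2/3, so the effective size is m = 60/(2/3) = 90 per arm. The pooled two-proportion power is

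Φ{[Δ√m − 1.96√(2p̄(1 − p̄))] / √(p₁(1 − p₁) + p₂(1 − p₂))}.

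For 80 vs 94%: Δ = 0.14, p̄ = 0.87, √0.2262 = 0.4756 and √0.2164 = 0.4652. So (0.14 × 9.487 − 1.96 × 0.4756)/0.4652 = 0.85, giving 80.3%. The other pairs give 80.5% (60 vs 79.2%) and 79.8% (70 vs 87%). A simulated logistic main effect over three time points, without interaction and with a robust Wald test, also gives about 80% at each pair. The printed figure therefore belongs to a time-averaged test on either scale.

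**Step 2: one time point, as in 9.6.** With m = 60, the same formula for 80 vs 94% gives (0.14 × 7.746 − 0.9322)/0.4652 = 0.33, or 62.8%. On the log-odds scale the difference is 2.7515 − 1.3863 = 1.3652, with standard error √[(1/0.16 + 1/0.0564)/60] = 0.632. Power is Φ(1.3652/0.632 − 1.96) = Φ(0.20), or 57.9%.

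Exact enumeration of two binomials of size 60, counting non-estimable data sets as not significant:

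| Pair | Score | Log-odds Wald | Not estimable |
|---|---|---|---|
| 60 vs 79.2% | 64.3% | 63.0% | about 0 |
| 70 vs 87% | 63.5% | 62.0% | 0.02% |
| 80 vs 94% | 64.3% | 58.1% | 2.4% |

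The last entry is 0.94^60 = 0.024. Losing the averaging costs about 16 points at every pair (80 − 64). The Wald scale then costs 1.3, 1.5 and 6.2 points. At 80 vs 94%, Wald power among estimable data sets is 59.5%. That is 4.8 points below the overall score figure, and 3.9 below the score test on those same data sets (63.4%). With both arms at 94%, type I error is 0.9% by Wald and 4.7% by score.

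**Step 3: averaging the contrasts of the interaction model.** Simulation at 80 vs 94% with r = 0.5 gives about 73–74% by Wald over three time points (about 6% not estimable). Over the two time points in 9.6 it gives about 70–71% (about 4.5% not estimable). The retention pairs stay at about 80% over three and fall to about 75–76% over two.

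**Step 4: the undefined decision rule.** For two Wald contrasts at 80 vs 94%, simulated power is about 75% if either may be significant unadjusted (type I error about 8% with both arms at 80%), 58% with Bonferroni, and 40% if both are required.

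**The case against.** Section 9.6 does not specify a Wald test; a score contrast satisfies its wording. That stands, so what can be faulted on the statistic is that it and the fallback are unnamed. The per-time-point shortfall remains under either test.

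A reader might infer that the 80% can only come from a two-proportion test, so that the log-odds scale is what breaks it. Step 1 shows otherwise: a time-averaged logistic main effect also gives about 80%. The scale matters only once each time point has its own contrast, and then noticeably only at 80 vs 94%.

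A reader might also infer that the test weakens steadily as MMORE succeeds. It does not. With TAU at 80%, exact Wald power is 58% at 94% in MMORE, 68% at 97% and 41% at 99%. The late fall comes from non-estimable data sets counted as failures; power when estimable keeps rising.

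Finally, it is tempting to say that 8-week retention will sit at the ceiling. Women enter "receiving medication for OUD treatment as part of prenatal care at a partner maternity care practice", and Section 2.1 reports discontinuation "with the greatest drop-off evident between 6 weeks and 3 months postpartum". This makes high 8-week retention plausible, but the protocol gives no 8-week rates, and its prenatal discontinuation range is 0–33%. Under assumed rates of 85 vs 97%, Wald power is 42% against 67% by score, with 16% not estimable; at 90 vs 98% it is 12.5% against 46%, with 30% not estimable. These show sensitivity and are not forecasts. At the planned average retention rates, empty cells are negligible.

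**Conclusion.** The concern holds in this form: the tests in 9.6 do not have the 80% power stated in 9.2. At a single time point, power is about 64% by score and 58% to 63% by Wald, chiefly because the averaging is gone. The additional Wald loss is about 6 points for abstinence at 80 vs 94% (4 to 5 among estimable data sets), with a 2.4% chance per time point of no estimate; it is 1 to 2 points at the retention pairs.

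These figures assume 60 analysed per arm, two-sided 0.05, exchangeable correlation 0.5 where time points are combined, and no covariates. The documents do not support a claim that the log-odds scale explains most of the shortfall, or that large losses for 8-week retention are established.

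**What to change.** In 9.6, keep the logistic GEE and its time points. State that arm contrasts will be tested with a generalised score test. Add that bias-reduced (Firth-type) estimation will be used if any arm-by-time cell has no failures or no successes, and that a covariate-standardised risk difference with its confidence interval will be reported alongside the odds ratio. Say which contrast is primary and, if both time points are tested, what counts as success.

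In 9.2, do not attach 80% to the per-time-point test. Restate power for the contrast actually tested: about 64% per time point by score, or 58% to 63% by Wald. If a time-averaged contrast from the interaction model is made primary and tested by Wald, give about 73–74% for abstinence over three time points, or about 70–71% over the two in 9.6.

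The cost is SAP wording and a little code, with no change to data collection or visits. The drawback is that the stated power becomes less favourable.
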